5.1 Assignment of Analysis Sets

Final decisions regarding the assignment of participants to analysis sets will be made during the review of study data and documented in the final list of important deviations, validity findings and assignment to analysis set(s) (see Section 4.6).

For purposes of analysis, the following populations are defined:

| Population | Description |
|---|---|
| Enrolled | All participants who sign the informed consent form (ICF) |
| Randomly assigned to study intervention | All participants randomly assigned to study intervention |
| Full analysis set (FAS) | All randomized participants. Participants will be analyzed according to the intervention they were randomized to. The only potential reasons for exclusion would be a clearly erroneously randomization, or major good clinical practice (GCP) violations, for example, a suspicion of fraud. |
| Safety analysis set (SAF) | All participants in the FAS who take at least 1 dose of study intervention. Participants will be analyzed according to the intervention they actually received. |
| Pharmacokinetic analysis set (PKS) | All finerenone-treated participants (with the exception of participants excluded on the grounds of critical GCP violations) with at least 1 valid finerenone plasma concentration and without validity findings which would interfere with the evaluation of the pharmacokinetic (PK) data. |
| Listing-only set | All participants enrolled who were not randomized or were excluded from the FAS. Their data is provided as individual participant data listings and will not be included in any statistical analyses. |

6. Statistical Methodology

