**Table 9–2 Populations for Analyses**

Population	Description
Enrolled	All participants who sign the informed consent form (ICF).
Randomly assigned to study intervention	All participants randomly assigned to study intervention.
Safety analysis set (SAF)	All participants randomly assigned to study intervention and who take at least 1 dose of study intervention. Participants will be analyzed according to the intervention they actually received.
Full analysis set (FAS)	All randomized participants. Participants will be analyzed according to the intervention they were randomized to. Only potential reasons for exclusion would be a clearly erroneously randomization, or major GCP violations, for example, a serious suspicion of fraud.
Pharmacokinetic analysis set (PKS)	All finerenone-treated participants (with the exception of participants excluded on the grounds of critical GCP violations) with at least 1 valid finerenone plasma concentration and without validity findings which would interfere with the evaluation of the PK data.

Abbreviations: GCP = Good Clinical Practice; PK = pharmacokinetic

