6.4 Safety

All analyses on safety and tolerability data will be performed in SAF.

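### SAP 5.1 makes the safety set a subset of the FAS, so a dosed participant excluded as randomised in error is left out of all safety tables, contrary to the protocol's definition

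*SAP*

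**What the plan says.** Protocol Table 9–2 defines the safety analysis set (SAF) as "All participants randomly assigned to study intervention and who take at least 1 dose of study intervention". FAS membership is not a condition. The same table describes the FAS as all randomised participants and adds: "Only potential reasons for exclusion would be a clearly erroneously randomization, or major GCP violations, for example, a serious suspicion of fraud".

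SAP 5.1 defines the SAF as "All participants in the FAS who take at least 1 dose of study intervention". Its grounds for leaving someone out of the FAS are "a clearly erroneously randomization, or major good clinical practice (GCP) violations, for example, a suspicion of fraud". It adds a listing-only set, "All participants enrolled who were not randomized or were excluded from the FAS", whose data are shown as individual listings and "will not be included in any statistical analyses".

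SAP 6.4 then states: "All analyses on safety and tolerability data will be performed in SAF". Protocol 9.4.2 likewise places all safety analyses in the SAF.

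Two other places in the SAP bear on this. Section 7.2, the log of changes from version 2.0 to 3.0, presents the new SAF definition as a clarification about participants with GCP violations and gives no other reason. Section 3 describes the FAS as all randomised participants apart from those with critical GCP violations, and does not mention erroneous randomisation.

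**The concern.** The two grounds for exclusion from the FAS differ in kind. A major GCP violation, such as suspected fraud, can make a participant's data untrustworthy, and that may justify leaving the data out of safety as well as efficacy. A clearly erroneous randomisation is a fault in how the participant entered the trial. It does not in itself make the adverse events, serious adverse events or laboratory values recorded after dosing unreliable. By making the SAF a subset of the FAS, the SAP treats the two alike.

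Safety and tolerability form a stated secondary objective. What is at stake is the completeness of the safety tables and their agreement with the protocol. The tables affected are those of SAP 6.4: adverse event frequencies, incidences per 100 person-years, the cumulative incidence of hyperkalaemia, laboratory threshold counts and vital signs.

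**Working it through.** No figure in the plan is in dispute, so the check is a comparison of the definitions as sets.

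**Step 1. The two safety sets.**
- Protocol SAF = randomised and dosed.
- SAP SAF = randomised and dosed and in the FAS.
- Difference = randomised, dosed and excluded from the FAS.

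**Step 2. Who is in the difference.** Under SAP 5.1 a participant leaves the FAS for one of two reasons, and neither depends on whether a dose was taken:
- (E) clearly erroneous randomisation;
- (G) major GCP violation.

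The difference is therefore the dosed participants in E together with the dosed participants in G.

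**Step 3. Where they go.** Everyone excluded from the FAS enters the listing-only set, which is barred from statistical analysis, and SAP 6.4 uses only the SAF. Dosed participants in E and G therefore contribute to no safety table. Under the protocol's definition they contribute to all of them.

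**Step 4. What the stated reason covers.** The log in SAP 7.2 refers to GCP violations, which is G. Nothing in the log, or elsewhere in the SAP, gives a reason for removing E from safety.

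**Step 5. Agreement within the SAP.**

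| Place in SAP | Grounds for exclusion named |
|---|---|
| Section 3, FAS | critical GCP violations |
| Section 5.1, FAS | clearly erroneous randomisation; major GCP violations |
| Section 5.1, PKS | critical GCP violations; validity findings that interfere with the PK evaluation |
| Section 7.2, reason for SAF change | GCP violations |

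Only the FAS row of 5.1 brings in erroneous randomisation. The pharmacokinetic set (PKS) is not tied to the FAS. A finerenone-treated participant randomised in error, with a valid plasma concentration, could therefore belong to the PKS and also to the listing-only set. Those two memberships conflict.

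**Step 6. Timing.** The protocol supplied is Amendment 2 of 16 May 2022. The SAP cites a protocol dated 26 October 2022. The SAF change is logged between SAP version 2.0 (24 February 2023) and version 3.0 (20 June 2024), after both protocol dates. That points to a change made in the SAP alone, but does not prove it.

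**Step 7. Scale.** The documents give no count. SAP Section 3 plans about 6000 randomised participants, so each 0.1% who were dosed and excluded from the FAS would be 0.001 × 6000 = 6 participants. Assuming 0.1% to 1% gives 6 to 60. This range is an assumption for scale only; nothing in the documents supports a particular rate.

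**The case against.** The strongest case for leaving the text alone has several parts.

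- **The participants remain visible.** Their data appear in individual listings. SAP 6.1.1 reports the numbers enrolled, randomised, in the FAS and in the SAF by treatment group, country and site, and validity findings by treatment group. This stands: they are missing from the tables, not from the report. But listings do not enter an incidence or a rate.
- **Assignment to sets is blinded.** SAP 4.1 has these decisions documented before unblinding, and nothing suggests that exclusion would differ by arm. This also stands. The point is about completeness and agreement with the protocol, not about biased selection.
- **The protocol delegates the matter and the change is logged.** Protocol 9.4 says the SAP will describe the analysis populations. That permits detail, and perhaps a change, but the logged reason does not reach participants randomised in error.
- **Excluding data affected by a serious GCP violation is legitimate.** Agreed, and the fix keeps it.
- **A later protocol may have changed the SAF.** This cannot be ruled out without the version of 26 October 2022.

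A reader might go further and infer that those randomised in error would be people ineligible on potassium or eGFR, so that the tables would understate hyperkalaemia and renal risk. The documents do not support this. Neither document equates erroneous randomisation with an eligibility breach. SAP Section 3 gives FAS membership as the reason for not randomising ineligible patients, which implies that such patients stay in the FAS and, if dosed, in the SAF.

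**Conclusion.** The conflict is real but narrow. As written, SAP 5.1 removes from every safety table any dosed participant excluded from the FAS as clearly randomised in error. The protocol supplied would keep that participant in, and the SAP's stated reason covers only GCP violations. SAP Section 3 and 5.1 also disagree on the grounds for FAS exclusion.

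The number affected is unknown and probably small, since both documents present FAS exclusion as exceptional. The conclusion rests on the text of the definitions and on the assumption that the protocol of 26 October 2022 did not alter the SAF.

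Two further inferences are tempting and should not be drawn:

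- **A count of lost deaths.** Someone might apply the expected whole-study mortality, 775/5500 = 14.1%, to an assumed number excluded. The excluded fraction has no basis in the documents. About 535 of the 775 expected deaths are cardiovascular, and Protocol 8.3.6 sends deaths from disease-related events to the outcome-event page, not the adverse-event page. Most adverse event tables are limited to treatment plus 3 days. All-cause mortality is itself an efficacy variable analysed in the FAS, so FAS exclusions leave that analysis under either SAF definition.
- **A wider exclusion for fraud.** The protocol's example refers to a serious suspicion of fraud, and the SAP's to a suspicion. This is an illustration under the same criterion of major GCP violations, and does not show that more participants would be excluded.

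**What to change.** In SAP 5.1:

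1. Define the SAF as all randomised participants who took at least one dose, analysed by treatment received, whether or not they belong to the FAS.
2. Allow one exception: participants whose data are judged unreliable because of a major GCP violation, decided and documented before unblinding. Show the main adverse event, serious adverse event and death summaries a second time with these participants included. State openly that this exception departs from the protocol's SAF, which has none.
3. Amend the listing-only set so that it no longer takes in dosed participants who remain in the SAF.
4. Align the account of the FAS in Section 3 with 5.1, and say what counts as a clearly erroneous randomisation.
5. Check the SAF definition in the protocol of 26 October 2022 and cite it.

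The cost is a few lines of SAP text, a changed population flag and one repeat of the main summaries if the exception is used. The drawback is that the SAF is no longer a strict subset of the FAS. The on-treatment analysis of the primary endpoint in SAP 6.2.1.5 uses the SAF, so the SAP should also say whether that analysis is restricted to participants in both sets.

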6.1 Population Characteristics

Population characteristic analyses, except for participant disposition, will be performed for the FAS, if not stated otherwise.

6.1.1 Disposition

The number of participants enrolled, randomized and valid for the FAS and SAF will be summarized overall and by treatment group, country/region and study site. The number of participants discontinuing each epoch, together with the primary reason for discontinuation will be presented by treatment group (post-randomization epochs only) and overall in separate tables. In addition, the number of participants with important deviations will be presented

overall, by country/region for each treatment group, and in total. The frequencies of each important deviation and validity finding will be presented by treatment group and in total.

6.1.2 Demography and Other Baseline Characteristics

Demography includes age (continuous and categorized by 40-<65, 65-<75, 75-<85, \geq 85), sex, race, pooled region (for stratified analysis and for subgroup analysis), body weight (continuous and categorized by <60, 60-<90, \geq 90 kg), body height, BMI (continuous and categorized by <30 vs. \geq 30 as well as by <18.5, 18.5 to <25, 25 to <30, 30 to <35, \geq 35 kg/m²), hip and waist circumference and waist-hip ratio, smoking history (never, former, current smoker) and alcohol consumption.

Other baseline characteristics include baseline

- LVEF (continuous and categorized by <60% vs. \geq 60% as well as <50, 50-<60, \geq 60%)
- NYHA Class (II, III, IV)
- index HF event (randomized during/at HF event, very recent (\leq 7 days from randomization), recent (>7 days - \leq 3 months), >3 months, no index; as well as \leq 7 days from randomization, >7 days - \leq 3 months, >3 months or no index event)
- type of (latest) index HF event with respective timing (hospitalization for heart failure, urgent HF visit, no index event)
- serum potassium (continuous and categorized by \leq 4.5 mmol/L vs. >4.5 mmol/L)
- eGFR (calculated by CKD-EPI formula, Japanese formula adjustment made for participants recruited in Japan; continuous and categorized by <60 vs. \geq 60 mL/min/1.73 m² as well as <45, 45 to <60, 60 to <90, \geq 90 mL/min/1.73 m²),
- serum creatinine (continuous)
- SBP (continuous and categorized by <90, 90-<130, 130-<160, \geq 160 mmHg)
- diastolic blood pressure [DBP] (continuous)
- heart rate (continuous)
- NT-proBNP (continuous)
- UACR (continuous and categorized by <30 vs. \geq 30 as well as <30, 30-<300, \geq 300 mg/g)
- history of LVEF<40% (yes [improved], no). For participants with a history of LVEF <40%, prior LVEF values will be summarized.
- Atrial fibrillation at baseline per ECG
- Diabetes Mellitus at baseline
- ACEI, ARB or ARNI use at baseline
- SGLT-2i use at baseline.

All demographic data and baseline characteristics will be tabulated by treatment group and overall. The demographic and other baseline characteristics table will also be presented, separated by each level of the stratification factors.

The non-stratified demographic and other baseline characteristics table will be repeated for the SAF if $\geq 5\%$ of randomized patients do not take at least one dose of study intervention (i.e. are in the FAS but not the SAF).

As stated in Section 4.2, demographics and other baseline characteristics will also be presented separately for participants prematurely discontinuing the study and for participants permanently discontinuing study treatment.

6.1.3 Medical History

Medical history will be coded using the Medical Dictionary for Regulatory Activities (MedDRA). Medical history will be presented for each MedDRA Primary System Organ Class (SOC) and Preferred Term (PT) by treatment group and overall in a summary table. Additional medical history terms by the following Standard MedDRA Queries (SMQs), Project-specific Bayer MedDRA Queries (PBMQs), Bayer MedDRA Labeling Groupings (MLGs) or selected PTs will also be presented:

- Hyperlipidemia (MLG)
- Hypertension (MLG)
- Type 2 diabetes mellitus (PT)
- Atrial fibrillation/flutter (PBMQ)
- Ischemic Stroke/Transitory Ischemic Attack (TIA) (PBMQ)
- Myocardial Infarction (MLG)
- Coronary Artery Disease (PBMQ)
- Peripheral Arterial Occlusive Disease (PBMQ)
- Cardiac Failure (MLG)
- Coronary Artery Bypass Graft (CABG) (PBMQ)
- Chronic Obstructive Pulmonary Disease (COPD) (PT)
- Percutaneous coronary intervention (PCI) (PBMQ)
- COVID-19 (SMQ narrow)
- Hepatic cirrhosis (PT)
- Sleep Apnea Syndrome (PT)
- Chronic Kidney Disease (CKD) (PT)

The medical history tables will be repeated for SAF.

6.1.4 Concomitant Medications

Concomitant medications will be coded using the World Health Organization Drug Dictionary (WHO-DD). The number of participants who took at least one concomitant medication and the number of participants who took at least one medication that started before administration of study drug will be presented by treatment group and overall using anatomical therapeutic chemical (ATC) classes and subclasses.

These tables will be repeated summarizing the number of participants with medications in the Standard drug groups of interest. In addition, the number of participants who took at least one concomitant medication that started after start of study drug and the number of participants who took at least one medication ongoing at baseline (i.e. starting before or on the day of randomization and ending at least one day after the day of randomization) will be presented by treatment group and overall. Standard drug groups of interest are:

- ACEIs and ARBs
- ARNIs
- Beta-blockers
- Loop diuretics
- Thiazide diuretics
- Digoxin
- Nitrates
- Potassium supplements
- Potassium lowering agents (including binders)
- Alpha blocking agents
- Calcium channel blockers
- Centrally acting antihypertensives
- Strong, unclassified, moderate, weak cytochrome P450 isoenzyme 3A4 (CYP3A4) inhibitors
- Strong, unclassified, moderate, weak CYP3A4 inducers
- Aspirin
- Statins
- MRAs
- Organic anion transporting polypeptides (OATP) substrates

Anti-diabetic drugs

- Insulin and analogues
- SGLT-2 inhibitors
- Other anti-diabetic drugs (Dipeptidyl Peptidase 4 inhibitors or Glucagon-like peptide-1 agonists or Biguanides or Sulfonylureas or Alpha glucosidase inhibitors or Metiglinides or Thiazolidinediones.)

A participant will be counted only once within each ATC class / subclass or Standard drug group, respectively.

A listing will be provided including all medications classified as a strong, unclassified, moderate, or weak CYP3A4 inhibitor according to the drug groupings together with the respective classification information.

For potassium lowering agents, ACEIs, ARBs, diuretics and SGLT-2 inhibitors shift tables for changes of use for baseline vs. any time treatment-emergent will be provided.

The number of participants with MRA use during follow-up will be given by substance.

6.1.5 Treatment and Study Duration, Extent of Exposure and Compliance

The analyses described in this section will be repeated for the SAF if $\geq 5\%$ of randomized patients do not take at least one dose of study intervention (i.e. are in the FAS but not the SAF). All tables and figures regarding treatment duration, extent of exposure and compliance will be presented by treatment group and overall (unless otherwise stated).

Treatment duration, defined as time from start of study drug to permanent stop of study drug (in months), will be summarized using descriptive statistics by treatment group and overall. The total duration in patient-years will be provided. In addition, treatment duration will be categorized to ≤ 1 month, 1 – 3 months, >3 – 6 months, >6 – 12 months, and then further six-monthly intervals, and presented with the corresponding number and percentage of participants. Cumulative treatment duration will be categorized to at least one dose, at least 1 month, at least 3 months, then further 3 monthly intervals. A table will be presented with the absolute and relative frequencies of participants still on study medication at each visit. Kaplan-Meier plots for “patients still on study treatment” will be provided, as also described in Section 4.2.

The above analyses will be repeated for study duration, from the day of randomization to the EoS visit.

The extent of exposure to study drug (total amount of intake in grams) and the average daily dose in mg during treatment will be summarized using descriptive statistics by treatment group. The table will be repeated by participants starting on 10 mg and 20 mg, respectively.

The number and percentage of participants on each dose level (blinded) will be summarized by visit and treatment group, overall and differentiated by participants starting on 10 mg or 20 mg. The overall titration status, regardless of actual or sham up-titration, will be summarized with absolute and relative frequencies per treatment group, overall and differentiated by patients starting on 10 mg or 20 mg. In addition, the number of patients with study drug down-titrated or temporarily interrupted (dose recorded as 0 mg) as well as associated reason will be summarized with absolute and relative frequencies per treatment group, overall and differentiated by participants starting on 10 mg and 20 mg, respectively.

The overall compliance (as a percentage) will be calculated as follows:

$$100 * \text{Number of tablets taken} / \text{Number of planned tablets.}$$

The number of planned tablets will be calculated as follows:

$$(\text{Days from randomization to last intake of study drug} + 1) * \text{Number of planned tablets per day.}$$

For participants who withdraw prematurely from the study drug, compliance will be calculated up to the time of last dose.

The overall compliance will be summarized descriptively by treatment group and overall. In addition, percentage compliance will be categorized into three groups, less than 80%, 80 to 120% and greater than 120%, and the categories will be summarized by treatment group and overall.

6.2 Efficacy

6.2.1 Analysis of Primary Efficacy Variable

Events that could potentially fulfill the criteria for primary efficacy variables during the study will be evaluated by the CEC. Definitions of individual endpoints (e.g. CV death) will be provided in the Endpoint Manual.

6.2.1.1 Primary Efficacy Variable: Primary Analysis

The primary Estimand as defined in Section 2 will be used for the primary analysis. The primary endpoint is the composite of CV death and total (first and recurrent) HF events (HHF or urgent HF visit) in HF patients. The primary analysis of this endpoint will be performed in the FAS using the planned treatment group, in line with the ITT principle.

Participants without an event of the primary composite endpoint at the time of analysis will be censored at the date of their last contact or date of non-CV death.

The number and incidence rate of primary endpoint events and censoring events (i.e. non-CV death) will be summarized per treatment group, both overall and per individual event category. 95% CIs of the incidence rates will be derived based on a Poisson model with robust variance estimator.

The primary analysis of the primary composite endpoint will be based on a stratified Andersen-Gill model (Andersen, 1982) including treatment group as fixed effect and including pooled region for stratified analyses and baseline LVEF ($<60\%$, $\geq 60\%$) as stratification factors. Robust standard errors (sandwich estimator) will be used to account for correlations of event times within a participant. As shown by Lin et al. 2000, the Andersen-Gill model with robust standard errors can be interpreted as a proportional rates model. After the authors of the paper, the model is also referred to as Lin, Wei, Yang and Ying (LWYY) model. Let θ be the RR for the finerenone versus placebo group. In order to evaluate whether finerenone is superior to placebo in reducing the rate of the composite event of CV death and total HF events the following null hypothesis will be tested using the model above (see Section 4.7 for details regarding the nominal significance level):

$$H_0: \theta = 1 \text{ versus } H_1: \theta \neq 1,$$

where $\theta < 1$ represents a treatment benefit of finerenone over placebo.

A point estimate of the RR together with a 95% CI will be presented alongside the point estimate and hazard ratio for the censoring event of non-CV death, calculated using a stratified Cox proportional hazards model.

The primary analysis method has been investigated with extensive simulation studies and it has been confirmed that it keeps the alpha level and has good operating characteristics across a range of plausible scenarios. A small adjustment will be made to the nominal significance level and the critical value at the final analysis to take into account the interim analysis (see Section 4.7 for details). No adjustment to the sample size calculation is done for this.

The SAS code below illustrates the program for the Anderson-Gill model:

```
PROC PHREG DATA=primary COVS (aggregate);  
  MODEL (time_start, time_rec)*status(0)=treat/ties=efron rl;  
  ID patid;
```

```
STRATA {stratum};  
RUN;
```

primary is the input dataset, time_start is the previous event stop time and time_rec is the current event stop time, the censoring variable status (0 for censored and 1 for event) should take the value 1 if the last event is a CV death and 0 if it is censored for a non-CV death or at the end of study for the given patient; patid is the participant ID and treat is the treatment group identifier.

If a participant experiences an HF event and subsequently dies for a cardiovascular reason, this will be considered as two separate events for the primary analysis unless the participant dies on the same calendar day as the HF event (both events would still be considered for the analyses of the separate components). If a participant is hospitalized for HF shortly after an urgent HF visit, this will be considered as two separate events for the primary analysis unless they occur on the same calendar day.

Additionally, plots and summaries of the mean cumulative function for the primary endpoint (Nelsen-Aalen estimate) will be presented by treatment group.

